Full Title	Prospective, multicentre clinical trial measuring the impact of treatment with ALVEOGYL in patients with post-extraction dry socket
Study medical device	Alveogyl
Study objectives	
Primary objective:
 
To measure the impact of Alveogyl treatment on pain at 7-day post-treatment.
 
Secondary objective:
 
To measure the impact of Alveogyl treatment on painkiller intake.
 
To measure the impact of Alveogyl treatment on healing.
 
To measure the impact of Alveogyl treatment on local inflammation.
 
To measure the impact of Alveogyl treatment on antiseptic effect.
 
To measure the impact of Alveogyl treatment on hemostasis.
 
To measure the safety and complication rate of Alveogyl treatment.

Primary outcome	Pain Visual Analog Scale (VAS) at 7 days post-treatment
Secondary outcomes	
- Painkiller intake: Analgesic use [Time Frame: at 3 days, 5 days and 7 days post-treatment]- Healing: Evaluation of healing of the alveolar mucosa. [Time Frame: at 7 days post-treatment].- Local inflammation: Signs of inflammation around the gingival mucosa (oedema, redness, sensitivity) [Time Frame: at 7 days post-treatment].- Antiseptic effect: Clinical signs (e.g., gum pain, swollen gum lining, fever, halitosis). [Time Frame: at 7 days post-treatment].- Hemostasis: presence or absence of bleeding [Time Frame: after Alveogyl placement].- Safety: Complication rate [Time Frame: From Alveogyl placement to 7 days post-treatment]
Study design and methods	ALVE study is a clinical investigation assessing Alveogyl performance and safety in patients with post-extraction dry socket. The study will take place in India and in France where the study device is already marketed. In India, the study is regulatorily considered as a pivotal clinical study in accordance with the Indian regulation. In France – European Union, the study is regulatorily considered as an observational, post-market clinical follow-up study with additional non-invasive and non-cumbersome procedures: the clinical investigation is under

	
the category “Other Investigation (Case 1: Clinical Investigation Post-Market Clinical Follow-Up)” in accordance with the European Medical Device Regulation (EU MDR).
 
Management of dry socket application protocol is at the discretion of the Investigator. Patients treated with the study device will be screened and eligible patients will be included in the study after obtaining their consent.
 
The primary outcome will be pain assessed by Visual Analog Scale (VAS) for adults at 7 days post-treatment. VAS is a 10-point line from “no pain” (0 point) to “worst imaginable pain” (10 points). A corresponding scale will be used for children as appropriate.
 
Additionally, patients will self-evaluate their pain level, their painkiller use and the feeling of Alveogyl (clove) taste at day 3 and day 5 at home.
 
All data will be recorded in either paper or electronic Case Report Form (CRF) and monitored by the Sponsor’s designee. Self-evaluation by the patients will be recorded in a paper datasheet.

Study population	
All patients with permanent teeth are eligible to participate into the study: Male and female patients, adults and children.
 
Note: Age of study population is defined by the permanent tooth requirement as first permanent teeth erupt on children.

Inclusion criteria	
 - Male or female patient, adult or child - Positive diagnosis of dry socket occurring after the extraction of a permanent tooth (mature or immature) - Signed informed consent - Patient affiliated to a Health Insurance Scheme (“sécurité sociale”)
Exclusion criteria	
 - Spreading infection in the alveolar socket - Placement of Alveogyl done immediately after tooth extraction - Multiple post-extraction dry sockets - Patient treated with cervico-facial radiotherapy - Immunodeficiency related to any diseases or current treatments - Psychiatric patient or patient unable to assess his/her pain via the study Pain VAS - Patient with history of hypersensitivity to one of the components - Patient on post extraction of deciduous teeth - Participation in another clinical investigation
Number of patients	
120 patients
 
It is estimate that about 90 patients will be included in India in about 10 investigational sites, and about 30 patients will be included in France in 2 investigational sites.

Follow-up(s)	
Patients will be evaluated at visit 1 – Day 0 and clinically followed at 7-day post-treatment (visit 2 – Day 7).
 
Some data will be collected at home, at Day 3 and Day 5: Pain VAS, painkiller use, and feeling of Alveogyl (clove) taste.

Study duration	
Patient enrolment will last 30 months (estimate).
 
Each patient's participation will last 8 days.
 
The entire study is expected to last 30.5 months.

Statistical analytic plan	
The assumption is that 92% of patients will have no pain or mild pain at Day 7 (primary outcome). This assumption is supported by the literature that reports a mean pain of 1.4 with standard deviation of 1.1 at Day 7, leading to a very large probability that patients have no pain / mild pain (VAS<4) at Day 7.
 
The sample size n=120 is based on the half-width (precision) of the 95% confidence interval of p=0.92: with n=113, the half-width will be 0.05 and 7 patients are added in case of a few non-evaluable patients.

Table 1: Schedule of Study Procedures

Study Phase	Visit 1	Patients' self-evaluation at home		Visit 2
TIMELINE	Day 0	Day 3	Day 5	Day 7
Informed Consent	X			
Review Inclusion/Exclusion Criteria	X			
Demographics/Medical History of interest	X			
Prior/Concomitant Medications of interest	X			
Clinical examination**	X			X
Pain evaluation based on VAS	X	X	X	X
Treatment with Alveogyl paste	X			
Evaluation of the presence of Alveogyl paste (via its clove taste) in the socket		X	X	X
Evaluation of painkiller use		X	X	X
Serious and non-serious adverse events assessment	X			X*
Device deficiency	X			X*

* Investigator will report at Visit 2 - Day 7 all safety issues (serious and non-serious adverse events and device deficiencies) which occur since Visit 1 -Day 0

** Including evaluation of the alveolus healing status, evaluation of the mucosa inflammation status, evaluation of bleeding status, and of the presence/absence of superinfection.

1 BACKGROUND AND RATIONALE

1.1 BACKGROUND AND RATIONALE FOR THE CLINICAL INVESTIGATION

Dry socket (or alveolar osteitis), is the most common complication following a dental extraction [1] and one of the most studied complications in dentistry [2]. The incidence of dry socket varies between 1% and 5% of all dental extractions, with up to 38% of dry socket cases associated with mandibular third molars [3], [4]. Dry socket develops as a postoperative complication when a blood clot fails to develop, dissolves, or dislodges at the site of the extraction before the socket is healed [5]. Socket that has been left exposed might be accumulated with food debris and bacterial biofilms that further hinder the healing process of the socket. Moreover, bacteria collected inside the socket may even ferment the food particles inside it, which in turn exacerbates the already compromised situation of the socket. Most commonly, patients suspected of suffering from dry socket present with acute pain from the exposed socket that lingers for many days until the socket is completely covered by the epithelium.

The treatment of alveolitis depends on each professional's clinical experience mainly due to the fact of its complex etiology. Traditionally, the treatment of dry socket has been irrigation, surgical intervention, and placement of medicated dressings.

Alveogyl (Septodont, Saint-Maur-des-Fossés – France) is a paste used as dressing in case of dry socket. Alveogyl has been sold and used worldwide since 2010; Alveogyl is one of the treatments advised for clinical management of alveolar osteitis.

Regulatory context in India:

Alveogyl is a Class B medical device according to current Medical Device Regulations (Medical Devices Rules 2017) and CDSCO Notice File NO. 29/Misc/3/2018-DC(85) dated 06/06/2018 Annexure 1.

In the context of recommendations of the Subject Expert Committee to perform a pivotal clinical investigation in India to support the registration of Alveogyl under the Drugs & Cosmetics Act 1940 & Rules 1945 and Medical Device Rules 2017, this study is put in place with the aim to confirm the safety and efficacy (performance) of Alveogyl in the treatment of dry socket.

Regulatory context in France and Europe:

Alveogyl is CE-marked as a class IIa medical device according to article 9 and rule 7 of the annex IX of Directive 93/42/EEC intended to be used in dentistry.

The results of this clinical study will be part of the clinical evidence for supporting the device claims and for CE-marking under the European Medical Device Regulation (MDR) 2017/745.

1.2 CLINICAL EVIDENCE TO DATE

In 2009, a double-blind, randomized, controlled pilot study in 106 patients has been performed to evaluate the performance and the clinical safety of two new pastes developed by Septodont: RD113/06

(35 patients) and RD113/08 (36 patients) in the treatment of dry socket in comparison to Alvogyl (35 patients). RD113/08 was the project name for the current commercialized and study device Alveogyl.

Results of the study showed that Alveogyl provides a favourable environment for the healing of the alveolar mucosa and is considered as safe for patients with a dry socket.

No publication exists on this study, only a clinical report in French is available upon request.

1.3 JUSTIFICATION FOR THE DESIGN OF THE CLINICAL INVESTIGATION

The study device Alveogyl is a paste already marketed and used in India and France for several years (8 years in India, 12 in France).

ALVE study is a clinical study assessing Alveogyl performance and safety in patients with post-extraction dry socket.

Efficacy of a method used for dry socket management is usually measured through the relief of patient's pain and the promote of alveolar mucosa healing [6]. The study objectives and outcomes measured were notably based on this information.

Additionally, the following clinical performance and clinical safety parameters claimed by the manufacturer for the study device will be verified through the results obtained in the current study:

- Provides a favourable environment for physiological tissue healing,
- Reduces pain,
- Reduces local inflammation and reduces risks of contamination due to its barrier effects.
- Hemostasis support

1.4 JUSTIFICATION OF THE CHOICE OF THE INVESTIGATION POPULATION

The target population for this study is the same as the intended population specified in the study device's instructions for use: patients with permanent teeth (mature or immature).

As permanent teeth can erupt in children (permanent teeth typically begin erupting around age 5), minors are eligible to participate in the study. Other vulnerable patients can be included in the study as there is no additional risk for this population.

1.5 RISK EVALUATION (RISK-TO-BENEFITS RATIONALE)

1.5.1 Anticipated clinical benefits

It is expected that Alveogyl provides the following clinical benefits:

- Pain reduction
- Inflammation reduction
- Limit infection with its barrier effect

1.5.2 Anticipated adverse events related to device or procedure

The following possible adverse events related to the device or to the procedure of dry socket treatment have been identified during clinical evaluation and risk analysis:

- Mouth ulceration,

- Pain,
- Paresthesia,
- Infections (osteitis, abscess),
- Swelling,
- Hypersensitivity/irritation reactions
- Local inflammation,
- Temporary fever,
- Bleeding gum,
- Delayed healing,
- Possible increased bone resorption (the material should be removed in the area that receives future implants),
- Ulceration.

1.5.3 Risks associated with participation in the clinical investigation

Septodont's last Clinical Safety Review analysis reported that Alveogyl is safe under the recommendation of use: there is indeed, up to 31-Dec-2020, only 22 reported cases out of 40 489 595 patients exposed. All the reported safety concerns retrieved are identified as either being associated with the dental procedure (i.e., paresthesia, dysaesthesia, pain) or to the product itself (irritation, hypersensitivity).

As the study medical device is used in its indication according to the Instructions For Use (IFU) with only collection of clinical data, there is no additional risks associated with patients participation in this clinical study. The patient will be treated as per standard practice and following the IFU (see Annex 1).

1.5.4 Possible interaction with concomitant medical treatments as considered under the risk analysis

There is no interaction with a concomitant medical treatment that may present a risk.

1.5.5 Steps that will be taken to control or mitigate the risks

All identified risks have been estimated and evaluated according to the risk management plan and the results are logged in the risk analysis table of the study device (see Annex 2).

Each risk has been reduced as far as possible, using risk control measures when possible. All the risk control measures have been implemented.

After implementation of all risk control measures, there is no unacceptable residual risk.

All the information for safety that has emerged from the risk analysis has been included in the instructions for use, including risk control measures and residual risks.

1.5.6 Rationale for benefit-risk ratio

The clinical risks of the study device are consistent with the state-of-the-art (based on competitors' products results in the same indication). The overall residual risk is considered acceptable.

The clinical evaluation of the study device concluded on a favourable benefit-risk ratio of Alveogyl in patients with dry socket as the product provides a favourable environment for physiological tissue healing.

The results of this clinical study should confirm the favourable benefit-risk ratio.

2 DESCRIPTION OF THE STUDY DEVICE

2.1 STUDY DEVICE

2.1.1 Description

The name of the study medical device is Alveogyl.

In India, Alveogyl is a Class B medical device according to current Indian Medical Device Regulations (Medical Devices Rules 2017) and CDSCO Notice File NO. 29/Misc/3/2018-DC(85) dated 06/06/2018 Annexure 1.

In Europe, Alveogyl is a CE-marked Class IIa medical device according to article 9 and rule 7 of the annex IX of Directive 93/42/EEC intended to be used in dentistry.

The product is commercialized in Europe since 2010 and in India since 2014 and is currently on the market in nearly 90 countries worldwide.

Alveogyl is a paste used as dressing to treat dry socket and is intended to be applied on the patient's dental socket by a dental professional only.

Composition and role of the materials are detailed in the following table.

Table 2: Composition of Alveogyl

Raw material	CAS number	Quantity (g/100g)	Role
[REDACTED]	[REDACTED]	[REDACTED]	[REDACTED]
Eugenol	[REDACTED]	[REDACTED]	[REDACTED]
Calcium carbonate	[REDACTED]	[REDACTED]	[REDACTED]
Mint natural flavor [REDACTED]	[REDACTED]	[REDACTED]	[REDACTED]
[REDACTED] Penghawar djambi fiber	[REDACTED]	[REDACTED]	[REDACTED]
Sodium dodecyl sulfate	[REDACTED]	[REDACTED]	[REDACTED]
[REDACTED]	[REDACTED]	[REDACTED]	[REDACTED]

The product is packaged in a jar containing 10g of Alveogyl as presented in the following picture.

Packaging level	Component	Raw material
Primary packaging	Glass bucket / jar	[REDACTED]
	Obturator	[REDACTED]
	Cap	[REDACTED]
Secondary/sales packaging	Card Box	[REDACTED]

Figure 1: Primary and secondary packaging of Alveogyl

2.1.2 Intended purpose

Dry-Socket Surgical dressing.

NOTE: Please refer to the IFU for more information.

2.1.3 Indications

Alveogyl is a paste used as dressing in case of dry socket.

NOTE: Please refer to the IFU for more information.

2.1.4 Patient population

Patient with permanent teeth (mature or immature).

NOTE: Please refer to the IFU for more information.

2.1.5 Users

For professional dental use only.

NOTE: Please refer to the IFU for more information.

2.1.6 Experience / Training needed

There is no special training needed to use the study device as it is a CE-marked device used for several years and already in the Indian and French market and has similar use as other pastes in the market.

2.2 MANUFACTURER

Septodont

[name]

3 STUDY OBJECTIVES AND ENDPOINTS

3.1 STUDY OBJECTIVES

3.1.1 Primary objective

To measure the impact of Alveogyl treatment on pain at 7-day post-treatment.

3.1.2 Secondary objectives

To measure the impact of Alveogyl treatment on painkiller intake.

To measure the impact of Alveogyl treatment on healing.

To measure the impact of Alveogyl treatment on local inflammation.

To measure the impact of Alveogyl treatment on antiseptic effect.

To measure the impact of Alveogyl treatment on hemostasis.

To measure the safety and complication rate of Alveogyl treatment.

3.2 STUDY ENDPOINTS

3.2.1 Primary endpoint

Pain Visual Analog Scale (VAS) at 7 days post-treatment

3.2.2 Secondary endpoints

Painkiller intake: Analgesic use [Time Frame: at 3 days, 5 days and 7 days post-treatment]

Healing: Evaluation of healing of the alveolar mucosa. [Time Frame: at 7 days post-treatment].

Local inflammation: Signs of inflammation around the gingival mucosa (oedema, redness, sensitivity) [Time Frame: at 7 days post-treatment].

Antiseptic effect: Clinical signs (e.g., gum pain, swollen gum lining, fever, halitosis). [Time Frame: at 7 days post-treatment].

Hemostasis: presence or absence of bleeding [Time Frame: after Alveogyl placement].

Safety: Complication rate [Time Frame: From Alveogyl placement to 7 days post-treatment]

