4.5 STUDY PROCEDURES

4.5.1 Visit 1 – Day 0

During this visit (same day as dry socket diagnostic and procedure of Alveogyl treatment), the following elements will be performed:

- Eligibility criteria: Prior to patients' enrolment into the study, patients' inclusion and exclusion criteria will be reviewed by the investigator.
- Patient informed consent: see §4.4
- Medical record review: which will be extracted from the patients' medical chart (i.e., Date of birth (MM-YYYY), gender, risk factors); medical information related to tooth extraction and dry socket before the procedure (such as date of tooth extraction, numbered of the extracted tooth, etiology of the tooth extracted, ...); Concomitant therapy.
- Clinical signs or symptoms: such as presence of gum infection/periodontitis, time after which the pain started, blood clot within the alveolar socket, halitosis, confirmation of the diagnosis of dry socket, local inflammation evaluation, bleeding evaluation,...
- Visual Analog Scale: pain assessment through the VAS before the procedure

Placement of Alveogyl use is done according to the instruction for use (IFU, Annex 1)

Before inserting the paste, the socket shall be re-examined.

The inside of the socket should be thoroughly cleaned (i.e., irrigated and/or curetted) to remove all debris.

Take a small pellet (about 0.20 g) of paste and place it gently into the prepared dental socket. Do not suture.

Note 1: The management of dry socket paste application protocol is at the discretion of the Investigator, knowing that there are available guidelines (e.g., Canadian Dental Association, 2013).

Note 2: For more details on the procedure of use, precautions and warnings see IFU.

The following information will be collected:

- Clinical signs or symptoms: medical information related to dry socket
- Procedure information: type of pre-Alveogyl treatment (curettage, cleaning, local anaesthesia etc.); feedbacks on the study device (manipulation, consistency, placement); Post-Alveogyl treatment information (local inflammation evaluation, bleeding evaluation,...)
- Visual Analog Scale: pain assessment through the VAS after the procedure

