5.4 STATISTICAL METHODS FOR PLANNED ANALYSES

A statistical analysis plan will be developed separately.

Quantitative data will be reported with n, n missing, mean, standard deviation (SD), median, minimum, maximum and 1st and 3rd quartiles.

Qualitative data will be reported as n, n missing and percentage (calculated over the non-missing data).

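### The hemostasis endpoint and its analysis do not condition on bleeding before placement, so the all-patient no-bleeding proportion cannot by itself support the hemostasis claim

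*Combined protocol and SAP*

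**What the plan says.** The secondary objective in section 3.1.2 is "To measure the impact of Alveogyl treatment on hemostasis". The endpoint that serves it, in section 3.2.2, is "Hemostasis: presence or absence of bleeding [Time Frame: after Alveogyl placement", with no condition on bleeding before placement. Section 1.3 names "Hemostasis support" among the parameters "claimed by the manufacturer for the study device will be verified through the results obtained in the current study".

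Entry (sections 4.3.1 and 4.3.2) rests on a dry socket diagnosis. No criterion mentions bleeding.

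Section 4.5.1 lists bleeding twice at Visit 1. In the list before the placement steps it gives "confirmation of the diagnosis of dry socket, local inflammation evaluation, bleeding evaluation". In the list after them it gives "Post-Alveogyl treatment information (local inflammation evaluation, bleeding evaluation". Between the two come the placement steps: "Before inserting the paste, the socket shall be re-examined", then cleaning of the socket by irrigation and/or curettage, then insertion. The footnote to Table 1 also puts bleeding status in the clinical examination.

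On analysis, section 5.4 says qualitative data are given as n, n missing and "percentage (calculated over the non-missing data". Section 5.4.2 describes bleeding just after placement in the included population. Section 5.4.4 reports hemostasis as number and proportions among the clinical signs at Day 7 and any intermediary visit. In that section a difference from D0 is planned for VAS only. A separate SAP is announced and is not among the documents.

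**The concern.** Stopping a bleed can be observed only in a socket that is bleeding when the paste goes in. A socket that was dry beforehand and stays dry adds to the no-bleeding count but says nothing about cessation. If most sockets do not bleed beforehand, the all-patient proportion is high whatever the paste does.

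The claim is named in the protocol as one the study will check. The study is treated as pivotal in India (section 4.1), and its results are to support the device claims for CE-marking under the European regulation (section 1.1). A high percentage that mainly reflects how few sockets bled could be cited as confirmation.

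**Working it through.** **The plan's own figure.** The documents give no expected rate, precision or success criterion for hemostasis. The one sample-size figure belongs to the primary endpoint, and it reproduces: n = 1.96² × 0.92 × 0.08 / 0.05² = 113.1, against the stated 113, plus 7 = 120. It has no bearing on hemostasis beyond setting N = 120.

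**Inputs.** N = 120 comes from section 4.2.3. The following are not in the documents and are assumptions:

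- b, the share of sockets bleeding just before placement: 10%, 20%, 40%.
- s, the share of those bleeding who have stopped after placement: 0 for an inert paste without spontaneous cessation, 80% for an effective one.
- No new bleeding among sockets that were not bleeding.

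**Formula.** All-patient no-bleeding proportion = (1 − b) + b × s. With s = 0 this is 1 − b.

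| b | Bleeding before, of 120 | All-patient proportion, s = 0 | All-patient proportion, s = 80% | Difference (b × s) |
|---|---|---|---|---|
| 10% | 12 | 108/120 = 90% (exact 95% CI 83% to 95%) | 0.90 + 0.08 = 98% | 8 points |
| 20% | 24 | 96/120 = 80% (72% to 87%) | 0.80 + 0.16 = 96% | 16 points |
| 40% | 48 | 72/120 = 60% (51% to 69%) | 0.60 + 0.32 = 92% | 32 points |

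Without b, an observed 90% cannot be interpreted. It is what an inert paste gives at b = 10%, and also what s = 50% gives at b = 20%: 0.80 + 0.20 × 0.50 = 0.90.

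**The conditioned rate.** Among patients bleeding before placement, the proportion no longer bleeding estimates s directly and does not depend on b. With about 80% stopping, the exact (Clopper-Pearson) 95% intervals are:

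- 12 at risk, 10/12: 52% to 98%
- 24 at risk, 19/24: 58% to 93%
- 48 at risk, 38/48: 65% to 90%

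**Are the data there?** Section 4.5.1 lists a bleeding evaluation on both sides of placement, so a before/after table needs no new item. What is missing is the timing. The first evaluation appears ahead of the cleaning step in the text, but only the VAS item in that list is explicitly tied to before the procedure. Cleaning can change bleeding status. A socket that was dry at examination but bled after curettage would be put in the wrong row of the table. The re-examination does not settle this, because the text mentions it ahead of the cleaning and names no bleeding record for it.

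**The case against.** The strongest reply is that nothing in the plan calls a dry socket a success. There is no responder definition, threshold or test, only a description. A reader might infer that every non-bleeding socket is scored as a hemostatic success. The documents do not say so; they list presence or absence and leave it there.

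A reader might also infer that the study has no means of examining the claim. That goes too far as well. Bleeding is listed before and after placement, and the announced SAP could still define an at-risk denominator. The convention of taking percentages over non-missing data is a general reporting rule and was not written as a hemostasis denominator.

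Two further objections have force. First, section 1.3 does not define hemostasis support, and preventing new bleeding after curettage could be part of it; for that reason the table should also show new bleeding among sockets not bleeding before. Second, with no control arm described, the conditioned rate does not isolate the paste. If a share c of bleeds stops unaided, an inert paste scores c in the at-risk group, not zero. The lack of a comparator is shared with the other performance endpoints.

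These points limit the conclusion but leave its core. No text in hand compares bleeding before with after, or restricts the denominator. The figures that are planned, read alone, cannot distinguish a paste that stops bleeding from a population that hardly bleeds.

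**Conclusion.** The point holds as a gap in the endpoint definition and analysis. The all-patient no-bleeding proportion does not condition on bleeding before placement, so it cannot by itself support the claim in section 1.3. With an inert paste it would read 90%, 80% or 60% at an assumed b of 10%, 20% or 40%, given no spontaneous cessation and no new bleeding. These values show the direction and form of the problem; its actual size depends on b, which the documents do not give.

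This concerns one descriptive secondary endpoint. The primary endpoint and the sample size are unaffected. Most of the remedy uses items already listed for collection.

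**What to change.** In sections 3.2.2 and 5.4.4 and in the SAP:

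1. Pre-specify a 2×2 table of bleeding before and after placement at Visit 1.
2. Report, with an exact 95% CI, the proportion no longer bleeding after placement among patients bleeding before it.
3. Report new bleeding after placement among patients not bleeding before it.
4. Keep the all-patient proportion as description only.
5. State when the pre-placement bleeding evaluation is made relative to socket cleaning. For the analysis, the preferable record is one made after cleaning and immediately before the paste is inserted.
6. Reconcile the time frames: section 3.2.2 sets the endpoint after placement, while section 5.4.4 analyses hemostasis at Day 7 and intermediary visits.

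Items 1 to 4 and 6 are text changes using evaluations already listed. Item 5 is a clarification, or at most one yes/no field at Visit 1. If the field is new, the protocol and CRF change in both countries, approval may be needed, and any patients already enrolled would lack it. The statistical price is a smaller denominator and a wider interval, such as 52% to 98% for 10/12. The report should also say that, with no control arm, the result is descriptive and cannot be attributed to the paste.
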